### 4.2 Study Design

[figure not shown]
This is a multicenter, open-label, Phase 2 study of NKTR-102 in subjects with solid tumors who received NKTR-102 in a prior Nektar-sponsored clinical study. Following completion of NKTR-102 treatment on a prior NKTR-102 clinical study, subjects will be assessed for eligibility. The Sponsor must assess eligibility criteria prior to enrollment of all subjects.

Eligible subjects will continue treatment with NKTR-102 at a dose of 145 mg/m^2 or less in a q21d schedule as outlined in Section 6.5. Subjects who previously received a dose of NKTR-102 at <145 mg/m^2 will continue at the lower dose in this study. Subjects who underwent dose reduction of NKTR-102 due to observed toxicity prior to participation in the Extension study (Protocol 11-PIR-09) will not be re-escalated to the previous dose level upon resolution of the toxicity. Dose escalation for NKTR-102 is not permitted.

NKTR-102 will be administered as an IV infusion over approximately 90 minutes ( $\pm$  15 minutes) on Day 1 of each 21-day treatment cycle. Disease assessments for tumor response and progression will be performed as per local standard of care until disease progression. Minimal disease evaluation data (best response and date of progression) will be collected within this protocol. Tumor measurements are not required; only an overall assessment of response or progression by the Investigator is required. Subjects may continue to receive repeated cycles of NKTR-102 on this protocol as long as there is evidence of disease control in the judgment of the Investigator or until there is unacceptable toxicity, death, withdrawal of consent by the subject, Investigator decision, subject non-compliance, lost to follow-up or study is terminated by the Sponsor. After discontinuation of NKTR-102, all subjects, except those who withdraw consent from further study follow-up, are to be followed for disease status (as applicable), subsequent anti-cancer therapy, survival status, and resolution of toxicity attributable to study drug (with contact by phone, through a clinic visit, or through review of medical records approximately every 12 weeks ( $\pm$  4 weeks)).

A schematic of the study design is presented in [Figure 1](#).

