#### **7.4 Quarterly Follow-up**

Approximately every 12 weeks ( $\pm 4$  weeks) following the End-of-Treatment visit, subjects will have their medical records reviewed and may be contacted to assess disease status, survival status, receipt of subsequent anti-cancer therapy, and resolution of all toxicity attributable to study drug. Disease status during follow-up will only be assessed if the subject has not demonstrated disease progression since receiving NKTR-102. Quarterly follow-up will continue until death, withdrawal of consent by subject, physician decision, lost to follow-up, or the study is terminated by the Sponsor.

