### 12.2 Endpoints and Planned Analyses

The primary endpoint of this study is assessment of safety for subjects receiving continued NKTR-102 therapy.

The MedDRA medical dictionary will be used to map the AE/SAE verbatim terms to specific system organ classes and preferred terms. The incidence and duration of AEs will be tabulated by MedDRA preferred term, system organ class, severity and relationship to study drug. The maximum intensity and frequency of AEs will be summarized by treatment (dose level). By-subject listings will be provided. No formal statistical testing is planned for AE or other safety and tolerability data.

Tumor response will be summarized by histological tumor type and tabulated using by-subject listings based on disease assessments from this protocol.

Other data will be tabulated using by-subject listings.

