7.6 Efficacy Analysis

Tumor response will be assessed by the investigator according to the frequency that patient's standard of care allows. Baseline will be the assessment at screening visit. Data on the best response and disease progression (per physician assessment) will be collected according to RECIST criteria version 1.1 (Eisenhauser et al., 2009). Tumor assessment and responses at the baseline and subsequent visit will be presented in a listing. Best overall response (BOR) by investigator assessment will be summarized. Time to progression and survival time will be calculated from first dose of original NKTR-102 study enrollment. Time to progression is defined as time from date of first dose of original NKTR-012 study to the 1st date of progressive disease (PD) per investigator assessment in current study. Patients without PD will be censored in last visit/follow-up date. Time to death is defined as time from date of first dose of original NKTR-102 study to death date. Patients without death date will be censored in last visit/follow-up date.

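### SAP 7.6 sets no limit at the start of subsequent anti-cancer therapy, so time to progression can run into time on the next drug and best response has no stated window

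*SAP*

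**What the plan says.** **SAP 7.6.** TTP starts at the first dose in the original NKTR-102 study and runs "to the 1st date of progressive disease (PD) per investigator assessment in current study". The only censoring rule for TTP is "Patients without PD will be censored in last visit/follow-up date". For response, the text is "Best overall response (BOR) by investigator assessment will be summarized", with no statement of which assessments qualify.

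**Protocol 4.2.** "Disease assessments for tumor response and progression will be performed as per local standard of care until disease progression". After NKTR-102 is discontinued, subjects "are to be followed for disease status (as applicable), subsequent anti-cancer therapy, survival status, and resolution of toxicity attributable to study drug", about every 12 weeks.

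**Protocol 7.4** (repeated in section 10.0 and Appendix 1, note k). "Disease status during follow-up will only be assessed if the subject has not demonstrated disease progression since receiving NKTR-102". The reasons for ending follow-up are also listed: "Quarterly follow-up will continue until death, withdrawal of consent by subject, physician decision, lost to follow-up, or the study is terminated by the Sponsor". Starting another cancer therapy is not among them.

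**Protocol 12.2.** "Tumor response will be summarized by histological tumor type and tabulated using by-subject listings based on disease assessments from this protocol". This too has no cut-off.

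**The concern.** Protocol 6.11.2 bars other systemic cancer therapy during treatment and says NKTR-102 should be stopped if a prohibited treatment is needed. On-treatment assessments are therefore largely free of other drugs, and switching falls in the post-treatment period. Protocol 5.3 gives several reasons for stopping other than progression, including toxicity and the investigator's decision. A subject who stops for one of these and moves to another drug is still in the current study, still progression-free, and still followed for disease status. The progression date or censoring date that SAP 7.6 uses can then fall on the next drug.

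Evaluating the efficacy of NKTR-102 is a stated secondary objective (Protocol 3.2, SAP 3.2). There is no control arm against which the effect of later therapy could be judged. If the contribution of the next drug is not shown separately, a reader of the TTP summary cannot tell how much of it belongs to NKTR-102.

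**Working it through.** The plan gives no figure to reproduce. SAP 6.1 says that neither hypothesis testing nor a specific sample size is required. The check is mainly a reading of the rules, with a calculation for scale.

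**1. TTP.** Take a subject who stops NKTR-102 for toxicity without progression and starts another drug.
- Disease-status follow-up continues, because progression has not occurred (Protocol 7.4).
- If progression is later recorded in the current study, SAP 7.6 takes that date as the event.
- If it is not, SAP 7.6 censors at the last visit or follow-up.
- In both cases the interval includes time on the next drug. This follows directly from the text.

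Subjects who progress before switching are not affected, because their event date is already fixed.

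**2. BOR.** The link is weaker.
- In favour: SAP 7.6 gives no window, Protocol 12.2 uses disease assessments from this protocol generally, and Protocol 4.2 and 10.0 run assessments until progression.
- Against: Protocol 7.2 places best-response collection under treatment days. Appendix 1 marks disease assessment at screening and, in brackets, at cycles. The quarterly column shows only survival follow-up, whose note k refers to disease status rather than response.
- So a post-switch response could be counted, but no visit is described that would routinely record it. If one were counted at N = 150, it would add 1/150 = 0.7 percentage points.

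**3. How many subjects.** The documents do not say. The nearest figure is BEACON (Protocol 2.1.2.5, Table 2): 47/425 = 11.1% stopped for adverse events. Applied to the planned maximum of 150, 150 × 47/425 = 16.6, or about 17. Of the 47, 13 were for diarrhea, under a mandatory stopping rule that the same section says later studies will not carry. Without them, 34/425 = 8.0%, and 150 × 0.080 = 12, a low figure because some diarrhea stops would still occur. Neither number says how many would go on to another drug.

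**4. Size and direction of the TTP shift (illustration, on assumptions).**
- Progression hazard on NKTR-102: λ = ln 2 / 4.7 = 0.1475 per month, from the 4.7-month median PFS in the Phase 2 breast cancer study (Protocol 2.1.2.2).
- A share p stops without progression and switches, at constant rate μ = λp/(1 − p).
- The hazard on the next drug is rλ.
- Under the SAP rule, S(t) = e^(−(λ+μ)t) + μ[e^(−rλt) − e^(−(λ+μ)t)]/(λ + μ − rλ).
- Censoring at the switch gives a median of 4.7 months and e^(−12λ) = 17.0% progression-free at 12 months.

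| p | r | Median TTP, SAP rule (months) | Progression-free at 12 months |
|---|---|---|---|
| 11.1% | 0.25 | 4.9 | 20.9% |
| 11.1% | 0.5 | 4.8 | 19.2% |
| 11.1% | 1 | 4.7 | 17.0% |
| 11.1% | 2 | 4.5 | 15.2% |
| 30% | 0.25 | 5.4 | 28.4% |
| 30% | 0.5 | 5.1 | 23.3% |
| 30% | 1 | 4.7 | 17.0% |
| 30% | 2 | 4.3 | 11.8% |

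The values of r and the 30% are assumptions with no source in the documents. The model also ignores that extension subjects are selected as progression-free. It shows only that the shift can go either way and is small at the BEACON-like share.

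**The case against.** **Counting progression regardless of later therapy is a legitimate treatment-policy choice.** This stands. Censoring at the switch has its own weakness, since subjects who switch may differ in prognosis. It is a reason to show both versions, not to replace one with the other. SAP 7.6 does not say that the treatment-policy reading was intended.

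**A reader might infer that responses on the next drug are credited to NKTR-102.** The documents do not support that. They leave the possibility open, but the schedule points to response being recorded at screening and cycle visits.

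**A reader might add BEACON's physician-decision stops (28/429 = 6.5%) to the adverse-event stops, then apply a response rate to count misattributed responders.** The text under Table 2 links physician-decision stops to clinical progression, so they cannot be taken as progression-free. No response rate for a later therapy appears anywhere. Such counts should not be used.

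**Protocol 9.5 allows follow-up of related adverse events to end when new cancer therapy starts.** That governs the length of safety follow-up. It does not show that efficacy was meant to have the same limit.

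**The stakes are low.** This is an access study with descriptive analyses, and Protocol 12.2 does not mention TTP. That stands, and it limits the weight of the point. Also, the SAP text available ends at 7.6 and its table and listing shells are not reproduced, so a cut-off stated there cannot be excluded.

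**Conclusion.** The point holds in limited form and is a cheap improvement. For TTP the reading is firm: with no limit at subsequent therapy, subjects who stop without progression and switch contribute time on the next drug. For BOR the finding is only that no window is stated.

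The number affected is not derivable. About 17 of 150 is a rough proxy that assumes BEACON adverse-event stop rates, full enrolment, no progression at stopping, and a switch by every such subject. At that share the illustrated median moves from 4.7 months to between 4.5 and 4.9, depending on the next therapy, and not at all if the next drug performs equally. A reader might infer a consistent bias in favour of NKTR-102; the documents do not establish a direction. No error rate or power is affected, because nothing is tested.

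**What to change.** In SAP 7.6:
- Limit BOR to assessments on or before the start date of subsequent anti-cancer therapy.
- Report TTP two ways: (a) subjects who start such therapy without progression are censored at their last disease assessment before that date; (b) the current rule, with progression counted regardless of later therapy. Label each.
- Leave time to death as it is.

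Before finalising, confirm that the case report form captures the start date of subsequent therapy and dated responses. Protocol 7.4 names only receipt of therapy, and Protocol 4.2 only best response and date of progression. If best response is held as one undated value it cannot be cut by date, although the by-visit listing in SAP 7.6 may supply what is needed. The concomitant-medication form is not a safe substitute: Protocol 6.11 covers it only to the End-of-Treatment visit, and SAP 7.4.1 says such data are not collected.

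Cost: SAP wording, minor programming and possibly one date field, or more if responses are not dated. Version (a) has a few more censored observations and possible informative censoring, which showing (b) beside it makes visible.

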## 7.2 Treatment Days

For all cycles, safety assessments are required before each treatment cycle. All results must be available before dosing. For all cycles, Day 1 assessments may be performed up to 5 days before Day 1. The following procedures will be performed prior to each dose:

- Symptom-directed physical examination, including body weight
- ECOG performance status
- Vital signs (pulse, temperature, blood pressure)
- Hematology and serum chemistry: minimally required are hemoglobin, ANC, platelets, and creatinine. Complete blood count and other laboratory tests will be obtained at the discretion of the Investigator.
- Body surface area
- Urine pregnancy test (only for WCBP)
- Assessment of concomitant medications
- Assessment of AEs
- Diarrhea must be fully resolved to NCI-CTCAE Grade 0 (a return to normal bowel movement habits) for at least 7 days without supportive antidiarrheal measures prior to treatment. Any treatment-related non-hematologic toxicities must have resolved to baseline or Grade 1
- NKTR-102 for Injection administration

**NOTE:** Disease assessment (tumor response and progression assessments) should be performed as per local standard of care. Best response and date of progression will be collected in this protocol. Other procedures and evaluations may be performed as clinically indicated and as determined by the investigator.

All safety laboratory evaluations will be performed at a local laboratory. Each laboratory must be certified and must be listed on the Statement of Investigator Form FDA 1572.

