## 7.3 End-of-Treatment Visit

The End-of-Treatment visit is to occur 30 days ( $\pm$  7 days) after last dose of study drug.

The following procedures will be performed for all subjects at the end of the subject's treatment:

- Complete physical examination, including body weight
- ECOG performance status
- Vital signs (pulse, temperature, blood pressure)
- Urine pregnancy test (only for WCBP)
- Assessment of concomitant medications
- Assessment of AEs

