## 10.0 EFFICACY EVALUATIONS

Due to the nature of this study, no specific schedule or type of tumor measurements/assessments are dictated within the protocol. These will be conducted as per the local standard of care until disease progression. Data on best response and disease progression (per physician assessment) will be collected according to RECIST criteria version 1.1 ([Eisenhauer et. al., 2009](#)).

Radiographs that document response, stable disease, or progression should be performed according to routine patterns of care and (preferably original) copies should be maintained by the Investigator for review by the Sponsor, if requested.

Approximately every 12 weeks ( $\pm 4$  weeks) following the End-of-Treatment visit, subjects will have their medical records reviewed and may be contacted to assess disease status, survival status, receipt of subsequent anti-cancer therapy, and resolution of all toxicity attributable to study drug. Disease status during follow-up will only be assessed if the subject has not demonstrated disease progression since receiving NKTR-102. Quarterly follow-up will continue until death, withdrawal of consent by subject, physician decision, lost to follow-up, or the study is terminated by the Sponsor.

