**17.0 APPENDICES**

**Appendix 1: Schedule of Assessments**

**Appendix 2: Cytochrome 3A4 Inhibitors**

**APPENDIX 1: SCHEDULE OF ASSESSMENTS**

Study Procedures	Screening Days -28 to -1	All Cycles a	End of Treatme nt c	Quarterly Follow-up	
		Day 1 b			
Informed Consent	X				
a Cycle length is 21 days.
 
b Any procedures that were completed as part of the end-of-study visit for the original protocol that match those procedures required during Screening may be used and do not need to be repeated if they were performed within 7 days of Cycle 1 Day 1 of this extension study. For all subsequent cycles, Day 1 assessments may be performed up to 5 days before Day 1. For all cycles, safety assessments are required before each treatment cycle. All results must be available before dosing.
 
c End-of-treatment visit to occur 30 ± 7 days after last dose of NKTR-102.
 
d There will be a complete physical exam with height and weight during Screening, symptom-directed physical exams with weight during treatment, and a complete physical exam with weight at the End-of-Treatment. Vital signs include pulse, temperature, and blood pressure. ECOG performance status will be assessed as part of the physical exam.
 
e Radiological exams or digital photography required during Screening unless subjects had disease assessment within 8 weeks prior to Cycle 1 Day 1 dosing. Disease assessments will occur during the study as per local standard of care (e.g., approximately every 6-12 weeks). CT or MRI scanning is acceptable for radiologic exams.
 
f If Grade 3 or 4 neutropenia is observed, more frequent CBC with differentials are recommended until Grade 1 or less.
 
g Minimally required: hemoglobin, ANC, platelets, and creatinine. Other tests obtained according to the Investigator’s discretion.
 
h Body surface area (BSA) will be determined before the start of each cycle, based on baseline height and most recent weight. Body surface area may be calculated based on institutional guidelines.

Eligibility Criteria	X				
Physical Examination, Vital Signs d	X	X	X		
ECOG Performance Status d	X	X	X		
Serum Pregnancy Test (for WCBP)	X				
Urine Pregnancy Test (for WCBP)		X	X		
Disease Assessment per standard of care e	X	[X]			
CBC f, g	X	X			
Serum Chemistry g	X	X			
Body Surface Area (BSA) h		X			
NKTR-102 Infusion i		X			

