5.0 OVERALL STUDY DESIGN AND PLAN

5.1 Study Design

[figure not shown]
This is a multicenter, open-label, Phase 2 study of NKTR-102 in subjects with solid tumors who received NKTR-102 in a prior Nektar-sponsored clinical study. Following completion of NKTR-102 treatment on a prior NKTR-102 clinical study, subjects will be assessed for eligibility. The Sponsor must approve enrollment of all subjects.

Eligible subjects will continue treatment with NKTR-102 at a dose of 145 mg/m² or less in a q21d schedule as outlined in Figure 1: Study Schematic. Subjects who previously received a dose of NKTR-102 at <145 mg/m² will continue at the lower dose in this study. Subjects who underwent dose reduction of NKTR-102 due to observed toxicity prior to participation in the Extension study (Protocol 11-PIR-09) will not be re-escalated to the previous dose level upon resolution of the toxicity. Dose escalation for NKTR-102 is not permitted.

NKTR-102 will be administered as an IV infusion over approximately 90 minutes (± 15 minutes) on Day 1 of each 21-day treatment cycle.

Subjects will continue to receive repeated cycles of NKTR-102 treatment until disease progression, unacceptable toxicity, death, withdrawal of consent by the subject, Principal Investigator decision, subject non-compliance, lost to follow-up, or study is terminated by the Sponsor. After discontinuation of NKTR-102, all subjects, except those who withdraw consent from further study follow-up, are to be followed for disease status (as applicable), subsequent anti-cancer therapy, survival status, and resolution of toxicity attributable to study drug (with contact by phone, through a clinic visit, or through review of medical records at least every 3 months) until death.

Figure 1: Study Schematic

a Pre-treatment safety assessments and NKTR-102 administration will occur on Day 1 of each cycle.

b Tumor assessments will be performed as required by standard of care.

c Treatment cycles will be repeated until disease progression, unacceptable toxicity, death, withdrawal of consent by the subject, Principal Investigator decision, lost to follow-up, or study is terminated by Sponsor (See Section 5.1).

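### SAP 7.6 censors time to progression at the last visit or follow-up date, which need not carry a disease assessment, so unassessed time can count as progression-free

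*SAP*

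**What the plan says.** SAP 7.6 runs TTP from the first dose in the original study to the first progression date given by the investigator in this study. The censoring rule is: "Patients without PD will be censored in last visit/follow-up date". For survival it is: "Patients without death date will be censored in last visit/follow-up date".

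On when disease is assessed:

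- Protocol 7.2 puts it in a note below the pre-dose procedures: "Disease assessment (tumor response and progression assessments) should be performed as per local standard of care". Appendix 1, footnote e, gives an example: "Disease assessments will occur during the study as per local standard of care (e.g., approximately every 6-12 weeks".
- Protocol 10.0 sets no schedule, but assessments do not stop with treatment: "These will be conducted as per the local standard of care until disease progression".
- Protocol 7.3 introduces the End-of-Treatment visit with "The following procedures will be performed for all subjects at the end of the subject's treatment". The list that follows has no disease assessment, and Appendix 1 marks none at that visit.
- Protocol 4.2 sets the standard of evidence: "Tumor measurements are not required; only an overall assessment of response or progression by the Investigator is required".
- After treatment, SAP 5.1 allows follow-up "with contact by phone, through a clinic visit, or through review of medical records at least every 3 months". Protocol 7.4 has disease status assessed at quarterly follow-up in subjects who have not progressed.

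**The concern.** The event is dated by a disease assessment, but the censoring time may come from any contact. A last-contact date suits survival, because contact shows the subject is alive. It suits TTP only if disease status was judged on that date. Otherwise the subject stays in the risk set as progression-free over a period in which nobody looked.

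Subjects without recorded progression are to be expected: Protocol 5.3 lists toxicity, withdrawal of consent, investigator decision, loss to follow-up and sponsor termination among the reasons for stopping. At stake is a TTP summary that reads too long, reported under the secondary efficacy objective (SAP 3.2).

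**Working it through.** The plan gives no TTP figure, sample size or event count to reproduce. The check uses its own visit intervals.

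**Inputs.** Cycle length 21 days (Protocol Appendix 1, footnote a). Example assessment interval 6 to 12 weeks (footnote e). End-of-Treatment visit 30 ± 7 days after the last dose (Protocol 7.3). Quarterly follow-up every 12 ± 4 weeks (Protocol 7.4).

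**Step 1. Which contacts carry a disease assessment?**

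| Last contact | Disease assessment on that date? |
|---|---|
| Dosing visit | Only if local practice places one there |
| End-of-Treatment visit | None listed |
| Quarterly follow-up | Disease status to be assessed if not yet progressed; phone or record review allowed, no imaging required |

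Nothing in the text available ties TTP censoring to an assessment date.

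**Step 2. Unassessed time while assessments stay on schedule.**

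- Maximum is one interval: 6 × 7 = 42 days; 12 × 7 = 84 days.
- Last contact a dosing visit, assessments on cycle Day 1 (assumption): 42/21 = 2 cycles, so the visit in between is 21 days after an assessment; 84/21 = 4 cycles, so the visits in between are 21, 42 and 63 days after. The maxima are 21 and 63 days. The dosing window and dose delays are ignored.
- Censoring date uniform within the interval (assumption): average 42/2 = 21 days or 84/2 = 42 days.
- At 30.44 days per month, 21, 42, 63 and 84 days are 0.7, 1.4, 2.1 and 2.8 months.

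**Step 3. Direction.** Assume a Kaplan-Meier summary, which the SAP does not name. Each event time contributes a factor 1 − d/n, with d events among n at risk. Moving censoring later leaves d unchanged and can only raise n. The curve therefore stays the same or rises compared with censoring at the last assessment. The per-subject gap is not itself the bias in the curve. If everyone shares one fixed assessment grid and nobody passes a due assessment, no event falls inside the gap and the curve does not move. It moves when schedules are staggered or assessments lapse.

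**Step 4. If assessments lapse when treatment stops.** This is less favourable than Protocol 10.0 intends. If the last dose falls 21 days (6-week interval) or 63 days (12-week interval) after an assessment, the End-of-Treatment visit is 21 + 30 = 51 days or 63 + 30 = 93 days after it (44–58 or 86–100 with the window). The first quarterly contact is 51 + 84 = 135 days or 93 + 84 = 177 days after it.

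A simulation of 50,000 subjects per scenario illustrates the effect. Assumptions: exponential TTP with median 4.7 months (the median progression-free survival in the Phase 2 breast cancer study, Protocol 2.1.2.2) or 12 months; exponential stopping with a 20% or 40% target for censoring (20.7% to 48.6% without recorded progression); assessments every 42 or 84 days, ending with treatment.

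| Censoring date | 12-month progression-free, median 4.7 mo | Median 12 mo |
|---|---|---|
| Last assessment | 0.189–0.197 | 0.525–0.531 |
| End-of-Treatment visit | 0.207–0.237 | 0.530–0.544 |
| One quarterly contact, no new assessment | 0.249–0.355 | 0.544–0.580 |

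Check on the first row: the last assessment day within 12 months is 336 on either grid (8 × 42 = 4 × 84). The expected values are 2^(−336/(4.7 × 30.4375)) = 0.196 and 2^(−336/365.25) = 0.529, which agree. Within scenarios, End-of-Treatment censoring raised the estimate by 0.005 to 0.040 and the quarterly contact by 0.018 to 0.158. The median was unchanged at End of Treatment in seven of eight scenarios (+1.4 months in the other) and rose by up to 2.8 months with the quarterly contact.

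**The case against.** The strongest reply is that the design covers much of this. Quarterly follow-up checks disease status in exactly the subjects who have not progressed, so a follow-up date is often an assessment date. On treatment, Protocol 4.2 allows further cycles only while the investigator sees disease control, and no measurements are required, so a dosing visit carries some disease information. Both points stand and narrow the problem. They leave dosing visits without a dated disease assessment, the End-of-Treatment visit, and contacts that yield nothing new on disease.

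Second, SAP 7.6 also uses the word visit for tumor assessments, so the rule might mean an assessment visit. The identical survival sentence makes that reading unlikely; at best the text is ambiguous and needs the same edit.

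Third, the SAP is written to amendment 2.0 of September 2013, while the protocol available cites data to May 2015. Visit content may have differed. But SAP 5.1 itself has tumor assessments following standard of care and permits phone or record-review follow-up, so the mismatch does not decide the point. The SAP's table shells and the CRF are not available.

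Fourth, the day counts rest on an example schedule, and the simulation on assumed censoring and on assessments stopping with treatment. True: they illustrate size and do not predict it.

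Last, TTP starts at the first dose in the original study and entry requires no progression since then, so time before entry is progression-free by selection. The censoring change does not repair that.

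**Conclusion.** The concern holds. Followed literally, SAP 7.6 can credit time after the last disease assessment as progression-free, and this tends to bias TTP upward. With assessments on the example schedule, the credited time per censored subject is at most 42 days (6-week interval) or 84 days (12-week interval). It averages 21 or 42 days if the censoring date is uniform within the interval, and is zero when disease status is assessed that day. Larger gaps require assessments to lapse. The effect on the reported summary cannot be fixed, because the documents do not give the share of subjects without progression.

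The consequence is modest. TTP is not a listed endpoint (Protocol 4.1.1, SAP 4.1), is not among the protocol's planned analyses (Protocol 12.2) and has no test (SAP 6.1). The rule should still be corrected, since SAP 7.6 commits to calculating TTP.

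**What to change.** In SAP 7.6, replace the TTP censoring sentence so that subjects without progression are censored at the date of the last investigator disease assessment showing none. Count any dated disease-status assessment obtained at quarterly follow-up. Keep the last visit or contact date for survival only.

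This is one sentence in the SAP and needs no extra scans. Confirm that the dates exist: Protocol 4.2 collects only best response and the progression date, while SAP 7.6 plans a listing of tumor assessments at baseline and later visits. If they are not captured, one date field must be filled from routine records, at up to 100 sites. The downside is that TTP may become slightly shorter and some subjects will be censored sooner.
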